13.2 Analysis of Results

The outcome of all patients who are registered onto this study will be reported. The results of patients in Cohorts 1, 2, and 3, will be summarized separately.

For those patients whose CE-MRI and mammography results suggested that they would be candidates for IORT (i.e. Cohort 1), the surgery results will be summarized in terms of whether or not a re-operation was indicated (because of inadequate margins or for any other reason) or whether or not WB-EBRT was recommended (because of small margin size or large tumor size, or another reason). For those patients who subsequently underwent re-excision +/- WB-EBRT or who subsequently received WB-EBRT alone (or mastectomy), all complications and side effects will be summarized.

For all patients, the size of the lesion as estimated by the imaging modalities will be compared to the size measured in the surgical specimen.

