3.0 STUDY DESIGN

- 3.1 Patients with biopsy proven-DCIS selecting WLE will undergo mammography and CE-MRI of the affected breast to evaluate the extent of disease. Patients will be deemed eligible for immediate IORT if the DCIS lesion is estimated to measure ≤4cm and is thought to be resectable with WLE and clear surgical margins. The DCIS lesion size determined by imaging will be compared with lesion size and surgical margin status obtained from the surgical pathology specimen to evaluate the ability of mammography combined with CE-MRI to identify suitable candidates for immediate IORT. For assessment of safety and tolerability of IORT (or other subsequent therapies), the study population will be divided into 3 cohorts:

Cohort 1: Patients who receive IORT at the time of initial WLE (the immediate IORT group).

Cohort 2: Patients who receive delayed IORT given at the time of a second operation, with or without re-excision of additional breast tissue (the delayed IORT group).

Cohort 3: This is the subset of patients in Cohort 1, who receive WLE and IORT, but who subsequently require WB-EBRT (with or without re-excision) or mastectomy.

3.2 Rationale for Inclusion of 3 Cohorts.

3.2.1 Rationale for Inclusion of Cohort 1. Several randomized and numerous non-randomized trials have been undertaken to evaluate the efficacy of APBI as an alternative to WB-EBRT to reduce recurrences after breast conserving surgery. For the most part, DCIS has been excluded from these trials due to the perceived difficulty in estimating lesion size based on clinical and mammographic findings alone. Since IORT is optimally administered at the time of WLE, prior to complete assessment of the surgical specimen, patients undergoing immediate IORT have a theoretically elevated risk of requiring additional therapy, for example, repeat WLE for inadequate margins. The present study has been developed to evaluate the ability of mammography combined with CE-MRI to identify suitable candidates for IORT, i.e., those who would have a low risk of needing additional surgery or radiotherapy.

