The cost of any additional imaging and cost of resulting procedures, if any, will be performed as part of the patient's routine preoperative evaluation and billed to her insurer. Alternatively, prospective participants may complete their imaging work-up by participating in an ongoing study at USC comparing bilateral breast CE-MRI, bilateral whole-breast ultrasound, and bilateral mammography (USC IRB Approved Protocol: Komen-06-01) which provides funding for these studies for uninsured or under-insured patients.

The major limitations of mammographic imaging of DCIS is that not all DCIS lesion form microcalcifications and among those that do, the span of calcification may not exactly correlate to the span of DCIS. High grade DCIS appear to show the best correlation between imaging findings and histological lesion size; low grade DCIS shows the worst correlation. In addition, a variety of microcalcifications (malignant, indeterminate, and benign type microcalcifications) may co-exist within

the breast, which can lead to over-aggressive or inadequate excision of breast tissues if the span of DCIS is judged incorrectly.

4.3 Contrast-Enhanced Breast MRI. CE-MRI of the breast will be required for all patients prior to determination of eligibility for IORT. CE-MRI of insufficient quality or those that were performed more than 60 days prior to determination of eligibility will be repeated.

Participants will undergo breast CE-MRI on a 1.5 or 3.0 Tesla MRI unit using a dedicated double breast coil. CE-MRI performed at other institutions will be permitted if they are performed on similar equipment and judged to be of appropriate quality. At USC, the following sequences will be obtained with the patient lying prone: (1) Scout-T1 FLASH—coronal/sagittal/axial (12 sec); (2) T2 TSE axial images of the breasts (3 min, 7 sec); and (3) T1 3d FLASH dynamic sequences (5 min, 30 sec including a pre-contrast sequence), contrast injection (15cc Gadolinium/20cc saline IV at 3cc/sec), a 20 second delay, and (4) pre-contrast images subtracted from last post-contrast images (the subtraction images), and (5) maximum intensity projections (MIP) of the subtraction images. Using the T2-weighted images and subtraction images, the area of maximal enhancement will be outlined and measured.

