5.3.2 Cohort 1 (Immediate IORT group)

- a. Localized DCIS measuring ≤ 4 cm on preoperative imaging.

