5.3.3 Cohort 2 (Delayed IORT group)

- a. Localized DCIS measuring ≤ 4 cm or less on surgical pathology

- i. Delayed IORT could be performed for the explicit purpose of administering IORT or performed following re-excision of a previously operated breast to achieve clear surgical margins.
- ii. This cohort includes patients who were excluded from immediate IORT based on pre-operative imaging suggesting ineligibility for immediate IORT, but who are subsequently found to meet histological criteria (localized DCIS ≤ 4 cm and no invasive cancer) for IORT based on surgical pathology.
- iii. Unifocal microinvasive (T1mic or invasive focus ≤ 1 mm in maximal diameter) is allowed following initial WLE if surgical pathology margins were ≥ 2 mm for both the invasive and non-invasive components.
- iv. Delayed IORT must be performed within 3 months of initial WLE.

5.3.4 Cohort 3

- a. Subjects who received IORT at the time of initial WLE but whose surgical pathology indicates the need for further therapy:
 - i. DCIS measuring greater than 5 cm on surgical pathology.
 - b. Surgical margins width < 2 mm.

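### Does comparing imaging size with specimen size in all patients let Cohort 2 hide underestimation in Cohort 1?

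*Combined protocol and SAP*

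**What the plan says.** The size comparison is one sentence at the end of section 13.2: "For all patients, the size of the lesion as estimated by the imaging modalities will be compared to the size measured" in the surgical specimen. It names no statistic and no rule for combining cohorts or modalities. Earlier in the same section stands the general reporting rule: "The results of patients in Cohorts 1, 2, and 3, will be summarized separately".

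The two enrolling cohorts have different size criteria. Cohort 1 (5.3.2) is selected on imaging: "Localized DCIS measuring ≤ 4 cm on preoperative imaging". Cohort 2 (5.3.3) is selected on the specimen: "Localized DCIS measuring ≤ 4 cm or less on surgical pathology". Item ii of 5.3.3 adds: "This cohort includes patients who were excluded from immediate IORT based on pre-operative imaging suggesting ineligibility for immediate IORT", provided that pathology then meets the criteria.

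Section 3.1 gives the purpose of comparing imaging with pathology: "to evaluate the ability of mammography combined with CE-MRI to identify suitable candidates for immediate IORT". On timing, section 4.3 says: "CE-MRI of the breast will be required for all patients prior to determination of eligibility for IORT". Section 10.1.2 defines extent of disease by mammography and CE-MRI done before the operation, set against the resection specimen, and places it among the additional data reported alongside the primary endpoint.

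**The concern.** Item ii works as a one-sided filter. A woman whose lesion reads above 4 cm on imaging enters Cohort 2 if pathology shows 4 cm or less, and never enters by this route if pathology confirms the large size. The cases in which imaging was right are removed, and those kept all show overestimation. Cohort 1 is filtered the other way: only readings of 4 cm or less enter, so lesions that imaging made too small are over-represented.

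Read literally, the phrase covering all patients invites one summary over both groups, in which the two selections offset each other. The background sections name underestimation as the cause of incomplete excision, so a pooled mean near or above zero could make imaging look safer than it is for choosing IORT candidates. A further worry is that women referred after excision elsewhere might have their CE-MRI when the lesion is already gone, so that it cannot measure it.

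**Working it through.** The documents attach no figure to this comparison, so there is none to reproduce. The check has four steps.

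**1. What is certain.** Let d = imaging size - pathology size. If imaging > 4 cm and pathology ≤ 4 cm, then d > 0. This needs no assumption, but it holds only for patients excluded on size and only for the modality that read above 4 cm. Section 3.2.2 allows exclusion on imaging or clinical findings, and sections 5.3.1 and 5.4 also exclude suspected invasion, multicentric disease and diffuse microcalcifications. Those exclusions say nothing about the sign of d. Aim 4 and 5.3.3(i) bring in women after a successful lumpectomy or for re-excision, whose entry does not depend on an imaging error.

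Mammography and CE-MRI are measured separately (4.2, 4.3). Assume two independent, median-unbiased modalities with log-error SD 0.2 to 0.4, and exclusion if either reads above 4 cm. A given modality then still underestimates in about 28 to 29% of the size-excluded patients.

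**2. What pooling would do.** Inputs: 79 patients in Cohort 1 (13.1.1) and about 20 in Cohort 2 (13.1.2). If k of the 20 entered on size under item ii,

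pooled mean = [79·d1 + k·d2 + (20 - k)·d3] / 99,

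where d1, d2 and d3 are the mean differences in Cohort 1, in size-excluded Cohort 2 patients and in other Cohort 2 patients. With k = 20, full cancellation needs d2 = (79/20)·|d1| = 3.95·|d1|; for d1 = -0.5 cm that is about +1.98 cm.

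Worked case (assumed: log-normal pathology size, median 2.5 cm, log-SD 0.5; unbiased additive imaging error, SD 1.0 cm). Simulation gives d1 = -0.17, d2 = +1.37 and d3 = -0.12 cm.

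- k = 20: (-13.43 + 27.40)/99 = +0.14 cm.
- k = 5: (-13.43 + 6.85 - 1.80)/99 = -0.08 cm.

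Ranges of the mean difference in cm (imaging minus pathology), all under assumed inputs:

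| Assumed imaging error | Cohort 1 alone | Size-excluded Cohort 2 | Pooled, k = 5 | Pooled, k = 20 |
|---|---|---|---|---|
| Additive, SD 0.5 to 1.5 cm, unbiased | -0.02 to -0.50 | +0.65 to +2.15 | -0.36 to +0.02 | -0.02 to +0.26 |
| Additive, same SD, bias -0.5 cm | -0.50 to -0.82 | +0.47 to +1.96 | -0.67 to -0.40 | -0.33 to -0.03 |
| Multiplicative, log-SD 0.2 to 0.4, mean-unbiased | -0.02 to -0.34 | +1.0 to +2.1 | -0.20 to +0.04 | +0.13 to +0.36 |

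The additive rows use median pathology size 2 to 3 cm and log-SD 0.5. The multiplicative row uses median 1.5 to 2.5 cm and log-SD 0.5 to 0.7.

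The share underestimated by more than 1 cm would, with k = 20, fall to 79/99 = 0.80 of its Cohort 1 value. For example, it falls from 0.327 to 0.261 with median 2.5 cm, bias -0.5 cm and SD 1.0 cm.

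So pooling always pushes the result upward. The sign turns reliably only if nearly all Cohort 2 patients entered on size and imaging is unbiased. Where imaging truly reads 0.5 cm low, the sign never turns.

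**3. Whether pooling is planned.** It is not. The general rule of 13.2 separates the cohorts, and no sentence asks for a combined size estimate. The phrase about all patients is met by making the comparison for every patient and tabulating it by cohort. The Cohort 1 column of the table then stands as it is. Cohort 1 is also the right group for the question in 3.1, since the imaging rule is applied to women whose lesions read 4 cm or less.

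**4. What depends on the comparison.** The accrual and go/no-go rules in 13.1.1 count re-excisions in Cohort 1 only (19 of 25, then 62 of 79, without re-excision). Section 13.2 also counts in Cohort 1 how often WB-EBRT was recommended for small margins or large tumor size. Clinically important underestimation is therefore counted directly. No test, threshold or decision is tied to the size comparison.

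**The case for a change.** The best case for a change is textual. The paragraph of 13.2 just before the size sentence limits itself expressly to Cohort 1, and the size sentence then turns to all patients. An analyst could take that as an instruction to combine. Even without pooling, the size-excluded part of Cohort 2 has its sign fixed by the entry rule, and nothing in 13.2 warns the reader. Limiting the comparison to Cohort 1 with pre-operative imaging, regressing pathology on imaging size, would cost only wording.

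Part of this stands. The sentence is thin, and size-excluded Cohort 2 patients cannot show how accurate imaging is. But the combined reading goes against the section's own reporting rule. Any tabulation by cohort shows the one-sided Cohort 2 differences for what they are.

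On timing, 10.1.2 already limits the comparison to pre-operative imaging. A scan taken after the first excision and before a second operation might be called pre-operative, but it could not be matched to the lesion in the first specimen, and an analyst would see that from the dates.

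The regression remedy has its own flaw. Section 5.1 requires 4 cm or less on both modalities, so a regression for one modality is distorted by selection on the other. With median 2.5 cm, log-SD 0.7 and median-unbiased log-error SD 0.4 (assumed), the slope falls from 0.86 to 0.71, and mean pathology size at a reading of 3 to 4 cm falls from 3.40 to 2.94 cm. Setting Cohort 2 aside would also lose the overestimation question that 3.2.2 gives as one reason for having that cohort.

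**Conclusion.** The selection effect is real but confined. It is certain only for Cohort 2 patients excluded on size, on the modality that excluded them, and their share of the roughly 20 is not stated. The harm to the Cohort 1 reading arises only if someone pools, which the plan does not ask for. Even then masking is usually partial: with 5 of 20 entering on size, the pooled mean moves by 0.04 to 0.15 cm from the Cohort 1 value in the additive scenarios. These sizes rest on assumed lesion-size and error distributions; the direction of the effect does not.

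Followed as written, the Cohort 1 size results, the re-operation rule and the WB-EBRT summary all remain sound. This is a gap in detail that a competent analyst fills by reporting sizes by cohort, listing Cohort 2 by entry route, and treating the Cohort 2 figures as descriptive. No amendment is needed.

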14.0 REGISTRATION GUIDELINE

Registration will be done with the Clinical Investigations Support Office into the Cancer Center database.

15.0 BIOHAZARD CONTAINMENT

No radioactive elements are used in the delivery of IORT. Background radioactivity will be actively monitored by the radiation physicist during the delivery of IORT to ensure patient and staff safety. WB-EBRT, if indicated, will be delivered per usual radiation oncology protocols established by the Radiation Safety Committee.

16.0 ETHICAL AND REGULATORY CONSIDERATIONS

All institutional and Federal regulations concerning the Informed Consent form will be fulfilled. The study will be conducted in adherence to ICH Good Clinical Practice.

Appendix I Philadelphia Consensus Guidelines for Classification of DCIS

A. Low grade nuclei (NG 1)

Appearance: Monotonous (*monomorphic*)

Size: 1.5-2.0 normal RBC or duct epithelial cell nucleus dimensions

Features: Usually exhibit diffuse, finely dispersed chromatin, only occasional nucleoli and mitotic figures. Usually associated with polarization of constituent cells.

Caveat: The presence of nuclei that are of similar size but are pleomorphic precludes a low grade classification.

B. High-grade nuclei (NG 3)

Appearance: Markedly pleomorphic

Size: Nuclei usually >2.5 RBC or duct epithelial cell nuclear dimensions

Features: Usually vesicular and exhibit irregular chromatin distribution and prominent, often multiple nucleoli. Mitosis may be conspicuous.

C. Intermediate grade nuclei (NG 2)

Nuclei that are neither NG 1 nor NG 3

Necrosis Quantification

Comedonecrosis: Any central zone necrosis within a duct, usually exhibiting a linear pattern within ducts if sectioned longitudinally.

Punctate: Non-zonal type necrosis (*foci of individual cells necrosis visible under 10X, 40X is not needed*)

Appendix 2 The USC/Van Nuys Prognostic Index scoring system for DCIS

Score	1	2	3
Size (mm)	≤ 15	16-40	>40
Margins width (mm)	≥ 10	1-9	<1
Pathologic Classification	Non-high grade Without necrosis (Nuclear grades 1 or 2)	Non-high grade with necrosis (Nuclear grades 1 or 2)	High grade with or without necrosis (nuclear grade 3)
Age	>60	40-60	<40
